The results from the initial demonstration and OEF/OIEF Veteran focus groups were used to inform the revisions of the transdiagnostic CBT protocol. Once the revised protocol was complete, a demonstration of the revised transdiagnostic CBT protocol was initiated, once again, within standard clinical psychotherapeutic practices at the VAMC. The methods of the second demonstration were largely identical to the first demonstration. Thirty-one VAMC patients were recruited to complete the treatment. All participants were diagnosed with multiple comorbid depressive/anxiety disorders and reported severe pre-treatment symptoms. Among the twenty-three treatment completers, PTSD was the most common principal diagnoses (39.1% PTSD, 26.1% MDD, 21.7% PD, 8.7% SOC, and 4.3% OCD) and MDD was the most common comorbidity (43.5% MDD, 26.1% PTSD, 8.7% drug/alcohol abuse, 4.3% PD, 4.3% SOC). Treatment completers attended an average of 11.8, 45-60 minute sessions. As presented in the table below, participants demonstrated significant improvements in symptoms of impairment/quality of life, depression, stress, anxiety, and PTSD across all disorders and comorbidities. These findings provide additional support for the feasibility and likely efficacy of the transdiagnostic CBT protocol for the depressive/anxiety disorders among VAMC patients.

Efficacy of Revised Transdiagnostic CBT in VAMC Patients

Scale (n)	Pre	Post	t (p)	Effect Size
IIRS-Impairment (23)	64.3 (13.1)	37.3 (17.6)	7.3 (<.001)	1.74
PTSD Checklist (22)	56.5 (17.8)	33.7 (14.2)	7.2 (< .001)	1.42
DASS-Depression (23)	12.0 (6.1)	4.8 (4.3)	6.7 (< .001)	1.36
DASS-Anxiety (23)	10.9 (5.4)	5.0 (3.5)	6.2 (< .001)	1.30
DASS-Stress (23)	13.8 (5.1)	7.0 (3.9)	6.1 (< .001)	1.50

Note. Sum scores reported as means (standard deviations). Cohen's ds used for effect sizes.

D. RESEARCH DESIGN AND METHODS

Project Timeline

Project Component	Year	Timeframe
Preparing for RCT	Y01	month 01 – 06
Hiring staff	Y01	month 01 – 03
Training on procedures/protocols	Y01	month 03 – 06
Advertising upcoming trial for recruitment	Y01	month 03 – 06
Randomized controlled trial	Y01-Y04	month 06 – 54
Recruitment and active treatment		month 06 – 45
Ongoing data entry and integrity/fidelity review	VS	month 09 – 42
Data analyses of post-treatment (follow-up)		month 24 – 54
Grant application(s) (e.g., DVA CSR&D Merit)	Y04-Y05	month 36 – 60
Dissemination of findings	Y05	month 54 – 60
Revision of manual based on findings/feedback	Y05	month 54 – 60

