RCT of Transdiagnostic CBT

Objective

To evaluate the transdiagnostic CBT in a RCT of VAMC patients with depressive/anxiety disorders by investigating its preliminary efficacy in reducing symptomatology, comorbidity, and improving quality of life compared to BAT (psychotherapy control condition) at immediate post-treatment and 6-month follow-up. Patient satisfaction and predictors of feasibility (attendance and dropout) also will be assessed.

Recruitment Strategy

VAMC patients will be recruited through the Primary Care – Mental Health Integration program and CBT Clinic at the RHJ VAMC. Within these programs, all VAMC patients reporting symptoms of depression and anxiety meet with a mental health staff member to complete a diagnostic interview and self-report measures as part of their standard clinical practices. If VAMC patients endorse symptoms consistent with a depressive/anxiety disorder, the patient's interest in participating in research will be assessed and, if agreeable to research, patients will be put in contact with research staff (same day meeting and/or follow-up phone to schedule research assessment). A research assessment will be completed with the project staff to first complete consent documentation and then assess inclusion/exclusion criteria (with a targeted sample of 96 VAMC patients; \geq 72 completers), including a semi-structured clinical interview and self-report questionnaires focused on the psychiatric symptoms and quality of life (described later). Participants who meet diagnostic criteria for the targeted disorders will be randomized into a study condition, and will be assigned to a project therapist. Because most VAMC patients who meet study criteria likely will present with multiple depressive/anxiety disorders, principal diagnosis, or the most impairing of

the diagnosable disorders, will be used to select patients for participation. To balance diagnoses across the two conditions, a stratified random assignment based on principal diagnosis will be used for the most common principal diagnoses (MDD, PTSD, and PD). Based on new patient consults at the RJH VAMC (i.e., nearly 1000 in 2011 with at least one-half presenting with symptoms of an depressive/anxiety disorder), it is expected that \geq 50% of the recruited VAMC patients will have served in OEF/OIF and \geq 33% will be representative of minority groups.

Eligibility Criteria

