~33	6-Month Follow-Up Assessment	Clinical interview, immediate treatment interview, & self-report battery (7 measures), treatment satisfaction

Note. Behavior therapy involves the introduction, teaching, in-session and between-session practice, and mastery of behavioral therapeutic techniques designed to improve symptoms of depression and anxiety, including behavioral activation (BAT group) as well as situational, physical, thought, and emotional exposures (transdiagnostic CBT group). Final treatment session will take place between sessions 12-16, as determined by provider and participants' collective decision. Final treatment session will involve relapse prevention content. Post-treatment assessment will be completed 1 week immediately after final treatment session. 6-month follow-up assessment will be completed 6-months after final treatment session.

Randomization Procedures

Participants will be randomly assigned (1:1) to one of the two study arms (*n* = 48 per arm) using a permuted block randomization procedure. Randomization will be stratified by principal diagnostic group and block size will be varied to minimize the likelihood of unmasking. After determining eligibility and completing consent and baseline assessment materials, enrolled participants will be assigned to treatment groups by the Project Research Assistant using a computer generated randomization scheme. Once a participant is randomized and attends the first session, they will be included in the intent-to-treat analysis. Randomization will occur at the participant level. As such, we will take the following steps to minimize contamination between the two arms of the study: 1) only one member of a household will be eligible for enrollment; and 2) other VAMC providers will be informed of their patients' participation in the study, but will be blinded to the treatment condition of their patients.

Transdiagnostic CBT Treatment Condition

As noted above in the Preliminary Studies section, a transdiagnostic CBT protocol was developed and revised through two demonstration studies and one focus group. The resulting protocol involves several primary components, including psychoeducation on the symptoms of depression and anxiety (session 1), assessment of motivation and setup of treatment plans (session 2), exposure therapy (sessions 3-15), and relapse prevention (final session). In addition to these primary components, optional modules are included to supplement exposure

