The full battery of self-report questionnaires and a diagnostic interview will be completed pre-treatment, immediate post-treatment, and at the 6-month follow-up to track participants' progression through treatment and maintenance. These time points for the assessments are consistent with CBT research with Veterans with depressive/anxiety disorders. To reduce the likelihood of missing data, all assessments will be scheduled separately from normal treatment sessions (intake appointment, one week following the final treatment session, and at 6-month follow-up). Additional staff training will be required prior to administration of the diagnostic interview. All assessments will be completed by the Project Research Assistant. All assessment staff will be required to observe the Principal Investigator administer the test twice and then administer the test twice themselves under the direct observation of the PI. All assessment staff will be blinded to treatment condition and supervised by the Principal Investigator. Assessments will be recorded to investigate inter-rater reliability. In addition to the pre- and post-treatment and follow-up assessments with the full battery, a brief assessment involving a few self-report measures (e.g., Depression Anxiety Stress Scales, Illness Intrusiveness Rating Scale, and State-Trait Inventory for Cognitive and Somatic Anxiety) will be completed biweekly to monitor symptoms during the course of treatment.

Albany Panic and Phobia Questionnaire (APPQ). The APPQ is a 27-item self-report measure that assesses agoraphobia, social anxiety, and interoceptive avoidance. Each subscale has been shown to have good internal consistency (α s > .85) and temporal stability (rs > .87).

Anxiety Disorder Interview Schedule-5 (ADIS-5). The ADIS-5 is a well-established, semi-structured interview designed to assess a wide range of Axis I disorders. The ADIS-5 assesses current and past diagnoses with DSM

diagnostic criteria, severity scores, and lists of feared and avoided situations for the anxiety disorders. The ADIS has demonstrated excellent inter-rater reliability and validity of depressive/anxiety disorder diagnoses.

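### No allocation concealment is described, and the role that conducts the screening and diagnostic assessments also assigns the arm, so selection bias at entry cannot be ruled out

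*Combined protocol and SAP*

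**What the plan says.** All places are in the combined protocol and SAP, section D unless noted.

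- **Who assigns.** Randomization Procedures: "enrolled participants will be assigned to treatment groups by the Project Research Assistant using a computer generated randomization scheme".
- **When.** The same sentence puts assignment at this point: "After determining eligibility and completing consent and baseline assessment materials". Allocation is 1:1 in permuted blocks within principal diagnostic group. Block size is varied, but the sizes are not given.
- **Who assesses.** Assessment of Mental Health Symptoms, Quality of Life, and Treatment Satisfaction: "All assessments will be completed by the Project Research Assistant". This includes the pre-treatment diagnostic interview. The section also says that assessment staff are blinded and are supervised by the Principal Investigator.
- **Who checks eligibility.** Recruitment Strategy: "A research assessment will be completed with the project staff to first complete consent documentation and then assess inclusion/exclusion criteria". No section names the person who makes the final decision on eligibility or principal diagnosis. Section E (Risks to the Subjects) has the qualifying diagnosis determined by the ADIS-5 at the pre-treatment assessment.
- **The stratum.** Recruitment Strategy: "a stratified random assignment based on principal diagnosis will be used for the most common principal diagnoses", naming MDD, PTSD and PD. Principal diagnosis is the most impairing of the patient's diagnosable disorders.
- **Comorbidity.** Section C reports of the revised-protocol demonstration: "All participants were diagnosed with multiple comorbid depressive/anxiety disorders". It says the same of the first.

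The plan describes no envelopes, central service or locked system.

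**The concern.** Concealment protects the step before randomisation: whether a candidate is entered, when, and in which stratum. It is a separate matter from blinded outcome rating, and the gap would remain if a different person did every post-treatment assessment. A varied block size makes guessing harder, but it does nothing for a list that the assigner can read.

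The documents leave three routes open to someone who knows or can guess the next arm:

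- **Timing.** Research contact may happen the same day or be scheduled later.
- **Eligibility.** Excluded patients may be looked at again once the reason for exclusion has settled.
- **Stratum.** Where several disorders coexist, naming the most impairing one is a judgement.

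The main claim is a between-arm difference against an active therapy, on seven self-report measures and with no multiplicity adjustment. Differences in prognosis created at entry could affect any of these measures, and also dropout and satisfaction. Adjustment for the pre-treatment score does not remove differences that were not measured, such as motivation.

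**Working it through.** **1. The plan's own figures.** None bears on concealment. The sample figures agree with each other: 2 × 48 = 96, and 72/96 = 75% completers. The plan states no power, effect size or SD.

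**2. What follows from the text alone.** The role that assigns knows each assignment it has made. The same role does the pre-treatment interviews of later candidates. Knowledge of past assignments at screening is therefore part of the written procedure. Whether that role also sees upcoming assignments is not stated.

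**3. Guessing the next arm from past assignments (illustration).** Assumptions:

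- Four strata of 38, 25, 21 and 12 patients. These are 96 × 39.1% (PTSD), 26.1% (MDD), 21.7% (PD) and the remainder, using principal diagnoses among the revised-demonstration completers.
- Block sizes drawn at random from the mix shown, because the plan gives none.
- Rule: guess the arm with fewer assignments so far in the stratum, and toss a coin if level.

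| Block sizes (assumed) | Correct guesses, g |
|---|---|
| 2, 4 | 0.715 |
| 2, 4, 6 | 0.695 |
| 4, 6 | 0.684 |
| 4, 6, 8 | 0.671 |
| 6, 8 | 0.663 |

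Chance is 0.50.

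**4. If the list were readable.** The next arm is then certain. For one patient who could credibly be placed in either of two strata, the chance that at least one stratum offers a given arm is 1 − 0.5² = 75%. With three strata it is 1 − 0.5³ = 87.5%. These figures describe a single such patient, not the trial.

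**5. From guessing to imbalance.** Let d be the prognosis gap, in SD, between patients entered when one arm is expected and those entered when the other is. The expected imbalance is d × (2g − 1), if selection operates throughout enrolment and before any covariate adjustment. The documents give no value for d.

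- d = 0.3: 0.3 × 0.326 = 0.10 SD, up to 0.3 × 0.430 = 0.13 SD.
- d = 0.5: 0.5 × 0.326 = 0.16 SD, up to 0.5 × 0.430 = 0.215 SD.

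**6. What a residual imbalance would do.** With 48 per arm and outcome SD 1, SE = √(2/48) = 0.204. For an imbalance b left after adjustment, the two-sided 5% type I error becomes 1 − Φ(1.96 − b/SE) + Φ(−1.96 − b/SE).

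| b (SD, assumed) | b/SE | Type I error |
|---|---|---|
| 0.05 | 0.24 | 5.7% |
| 0.1 | 0.49 | 7.8% |
| 0.2 | 0.98 | 16.5% |
| 0.3 | 1.47 | 31.2% |

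**The case against.** The strongest reply is that the plan is silent on concealment, and silence does not show that it is absent. A computer scheme that releases one assignment at a time fits the same words. **This stands.** A reader might infer that allocation is open and that patients will be steered. The documents do not support that.

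A reader might also infer that the Research Assistant alone judges eligibility and principal diagnosis. No section says so. The eligibility check is given to project staff, and the Principal Investigator supervises assessment. Discretion is limited in other ways:

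- clinic staff have already done a diagnostic interview;
- several exclusions rest on the medical record;
- the ADIS-5 is semi-structured with severity scores;
- assessments are recorded for inter-rater reliability.

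These make a re-labelled stratum easier to notice, but they do not conceal the sequence.

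Varied block size is not the only safeguard, because assignment already follows eligibility and baseline. That order limits later changes. It does not help if the next arm is known or guessed while eligibility is being settled.

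The analysis also adjusts for more than the pre-treatment score: age, comorbidity count, race, sex and baseline variables found to differ. This would shrink the figures in step 5 by an unknown amount. No motive or direction is shown either, since therapy is delivered by a separate project therapist.

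Finally, the same two sections already conflict on assessor blinding, and taking assignment away from the Research Assistant helps with both problems. The overlap is real, but correcting outcome rating alone would leave entry unprotected.

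**Conclusion.** The point holds as a risk that the written procedure leaves open. One role conducts the assessments that inform eligibility and stratum and also makes the assignment, and no concealment is described. That goes beyond a missing detail, because the combination of duties is stated.

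It does not hold as a finding that allocation is unconcealed or that every outcome is biased. The size and direction of any bias cannot be derived from the documents. The 66–72% guessing rate rests on assumed block sizes and stratum shares. The imbalances of roughly 0.10 to 0.215 SD also need an assumed prognosis gap of 0.3 to 0.5 SD and selection throughout enrolment, and they are before covariate adjustment. They illustrate what is possible and are not estimates for this trial.

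The change should be made: it is cheap, and unmeasured selection at entry cannot be repaired in the analysis.

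**What to change.** Keep the permuted blocks, strata and varied block sizes. Revise Randomization Procedures as follows:

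1. State who generates the sequence: someone who takes no part in screening or assessment.
2. Hold it in a form that the Research Assistant cannot read, such as a locked allocation module or sealed numbered envelopes.
3. Record eligibility and principal diagnosis, and lock them with a date stamp, before an assignment is released.
4. Release the assignment to an existing role outside assessment, for example the project therapist, who must know the arm anyway. Do not release it to the Research Assistant.
5. Allow no later change of the stratum used for randomisation.

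The cost is one paragraph, a small set-up task and a slightly slower hand-off. N stays at 96. If concealment already exists, stating it takes a sentence, but the assigning role should still be separated from assessment.

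This removes one source of the conflict with assessor blinding, but not all of it. Under Post-treatment Participant Interviews, the Research Assistant interviews the completers of the transdiagnostic CBT arm, and so would still learn those arms after treatment. Recruitment and treatment run together from month 06 to month 45, so this can happen while patients are still being entered. Varied block sizes therefore remain necessary.

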participants referred to this clinic already have expressed interest in receiving psychotherapy; and, thus, none of the 15 invited participants refused to participate in treatment. All participants were diagnosed with multiple comorbid depressive/anxiety disorders and reported severe, pre-treatment symptoms of anxiety and depression. PTSD was the most common presenting problem (46.6% PTSD, 26.7% SOC, 26.7% PD, 7.1%) and MDD was the most common comorbid disorder (64.2% MDD, 14.3% SOC, 7.1% PTSD, 7.1% PD). In general, participants were stabilized on multiple psychotropic medications prior to beginning CBT. Twelve of the fifteen participants finished treatment (80.0%). Treatment completers attended an average of 11.5, 50-minute sessions. As presented in the table below, participants demonstrated significant improvements in symptoms of impairment/quality of life, depression, stress, anxiety, and PTSD across all disorders and comorbidities. These findings provide preliminary support for the feasibility of a structured, transdiagnostic CBT protocol for the depressive/anxiety disorders among VAMC patients.

Scale (n)	Pre	Post	t (p)	Effect Size
IIRS-Impairment (12)	66.0 (14.9)	41.2 (19.8)	6.4 (< .001)	1.42
PTSD Checklist (7)	56.1 (13.1)	37.0 (14.0)	5.6 (< .01)	1.41
DASS-Depression (12)	26.2 (10.8)	10.3 (10.3)	5.3 (< .001)	1.51
DASS-Anxiety (12)	25.2 (10.7)	11.8 (9.1)	5.5 (< .001)	1.35
DASS-Stress (12)	26.3 (10.8)	15.7 (9.6)	3.6 (< .01)	1.04

Efficacy of Initial Transdiagnostic CBT in VAMC Patients

Note. Sum scores reported as means (standard deviations). Cohen's ds used for effect sizes.

Focus Group with OEF/OIF Veterans

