The full intent to treat (ITT) analysis set will comprise all randomized participants. Missing data in the full analysis set will occur if participants drop out prior to the end of the study. Participants will not be discontinued from the study because of non-adherence and all will remain in the study unless consent is withdrawn or if there are concerns regarding participant safety. Missing data for the ITT analysis set will be imputed using multiple imputation methods. The results of analyses using study completers and protocol adherers (completer and perprotocol analyses) will be compared with results using the ITT analysis set to test sensitivity of study conclusions to study drop-outs and protocol non-adherence. In addition, the information on dropout proportion will be used as one of the outcome measures of intervention feasibility.

Efficacy (Symptomatology & Quality of Life) Measures Analyses (Primary Aim 1)

The continuous measures of intervention efficacy and quality of life are APPQ, DASS, IIRS, MASA, PCL, STICSA, and V/SF-36. The primary outcome time point is at the end of the active intervention phase (immediate post-treatment) and the secondary time point is at the end of the naturalistic 6-month follow-up period. The difference in mean change from baseline to end-of-active intervention (effect sizes) for transdiagnostic CBT versus BAT control condition will be estimated via 95% CI. For the secondary time-point analyses, transdiagnostic CBT versus BAT control differences in change from immediate end-of-intervention to the 6-month follow-up will also be estimated using 95% CI. By assessing the magnitude of the between-intervention-group differences, as described by the CI, clinicians can judge whether the novel intervention provides sufficient improvement in these outcomes to suggest a clinically significant result that warrants further investigation.

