Measures of feasibility and acceptability are dropout proportions (dropout y/n), proportion of sessions attended, proportion of homework assignments completed, and patient satisfaction scores on the STTS-R. 95% CI for proportions will be used to estimate the proportion of participants who exit the study prematurely (drop out) within each intervention group and the difference in dropout proportions between the intervention groups. For the treatment satisfaction and adherence outcomes (STTS-R, proportion of missed sessions or homework assignments), the median and mean responses will be obtained within and between each intervention group. 95% CI for difference in means will be used to estimate the between intervention differences in treatment satisfaction (mean STTS-R) and adherence (e.g. average proportion of missed sessions or homework assignments) for the transdiagnostic CBT versus BAT control conditions. Frequency distributions describing the participants' reasons for noncompliance and discontinuation of participation will be developed.

The GLMM modeling framework described for Primary Aim 1 will be used to compare the effect of transdiagnostic CBT versus BAT control on treatment satisfaction, retention (dropout), and treatment adherence (% missed sessions, % homework completion). Dropout proportions (dichotomous outcome) and % of missed visits and % homework completion will be compared between the intervention groups using GLMM, with logistic/binomial regression analyses as special cases for dichotomous and percentage outcomes; STTS-R will be modeled as a continuous outcome using an appropriate link function. We also will model the longitudinal profile of adherence as a dichotomous outcome at each visit (e.g. attended/did not attend a given session). This will allow us to evaluate the trends in session attendance and to determine if the trends differ by intervention (e.g. whether the probability of missing visits is less/greater at earlier or later time points).

Exploratory Analyses - Diagnostic Groups

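### The protocol gives two definitions of the intent-to-treat set, one of which appears to drop randomised participants who never attend session 1

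*Combined protocol and SAP*

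**What the plan says.** Two current sections of the combined protocol and SAP describe who is in the intent-to-treat analysis.

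- **Section D, Randomization Procedures:** "Once a participant is randomized and attends the first session, they will be included in the intent-to-treat analysis".
- **Section D, Missing Data (within the Analysis Plan):** "The full intent to treat (ITT) analysis set will comprise all randomized participants". Multiple imputation is tied to this set. The only other sets named are completers and protocol adherers.

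On timing, Randomization Procedures says: "After determining eligibility and completing consent and baseline assessment materials, enrolled participants will be assigned to treatment groups". The Table of Procedures puts the pre-treatment assessment in week 1 and session 1 in week 2.

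On the Aim 2 outcomes, Missing Data adds that "the information on dropout proportion will be used as one of the outcome measures of intervention feasibility". The Feasibility and Acceptability Analyses section plans confidence intervals to "estimate the proportion of participants who exit the study prematurely (drop out) within each intervention group". It also lists the proportion of sessions attended as a measure and says: "We also will model the longitudinal profile of adherence as a dichotomous outcome at each visit". That section does not explicitly name an analysis set for dropout or attendance.

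**The concern.** The two statements carry the same label but can describe different people. Anyone randomised who never comes to session 1 is in the set under Missing Data and, on the natural reading, outside it under Randomization Procedures. Nothing in the document ranks the two.

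The attendance condition matters because it is applied after randomisation and overlaps with an outcome. Hypothesis 2 predicts better attendance and dropout in the transdiagnostic arm. If session 1 attendance is the entry ticket, it is 100% in both arms by construction. The per-visit attendance model then cannot show failure to start, although it is meant to show whether missed visits cluster early or late. Dropout is also understated, provided never-starters would otherwise count as dropouts.

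For Aim 1, leaving out never-starters could bias the between-arm comparison if never starting differs by arm. The documents do not show that it will, or in which direction. At the least, two analysts following this protocol could each report an ITT analysis on different participants.

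**Working it through.** **Step 1: compare the texts**

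| Section | Condition for the ITT analysis | Never-starter included? |
|---|---|---|
| Randomization Procedures | randomised and attended session 1 | no, on the natural reading |
| Missing Data | randomised | yes |
| Feasibility and Acceptability Analyses | analysis set not named | not stated |

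Assignment follows baseline (week 1) and session 1 is in week 2. The sets coincide only if nobody misses session 1.

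**Step 2: inputs for an illustration**

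- Planned sample: Recruitment Strategy, "with a targeted sample of 96 VAMC patients". Randomization Procedures gives 48 per arm, and 2 × 48 = 96.
- Completers: at least 72 (Recruitment Strategy), so at most 96 − 72 = 24 non-completers, and 24/96 = 25.0%.
- Number who never start, *k*: **not in the documents; assumed** to be 0, 1, 4, 8 or 12 in total.
- Simplification: all 24 non-completers, never-starters included, are treated as dropouts. The protocol does not equate the two terms.

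**Step 3: formulas**

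- Dropout among all randomised: 24/96.
- Dropout among session 1 attenders: (24 − *k*)/(96 − *k*).
- Session 1 attendance among all randomised: (96 − *k*)/96. In the attender set it is always 100%.
- Inflation of the mean proportion of sessions attended, with never-starters contributing zero: 96/(96 − *k*).

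| *k* (assumed) | Share of randomised | Dropout, all randomised | Dropout, attenders only | Session 1 attendance, all randomised | Inflation of mean attendance |
|---|---|---|---|---|---|
| 0 | 0% | 25.0% | 24/96 = 25.0% | 100% | 1.00 |
| 1 | 1.0% | 25.0% | 23/95 = 24.2% | 99.0% | 1.01 |
| 4 | 4.2% | 25.0% | 20/92 = 21.7% | 95.8% | 1.04 |
| 8 | 8.3% | 25.0% | 16/88 = 18.2% | 91.7% | 1.09 |
| 12 | 12.5% | 25.0% | 12/84 = 14.3% | 87.5% | 1.14 |

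**Step 4: an unequal split between arms**

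Assume 12 of 48 drop out in each arm, so the true difference is zero. If 5 of the 12 never start in one arm and none in the other, the attender set gives 7/43 = 16.3% against 12/48 = 25.0%. That is an apparent difference of 8.7 percentage points, favouring the arm with the no-shows. The 5-to-0 split is assumed and shows only the mechanism.

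**Step 5: can the pilot bound *k*?**

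The nearest figure is in Preliminary Studies: "none of the 15 invited participants refused to participate in treatment". Declining an invitation is not the same event as missing session 1 after randomisation. Even taken at face value, 0/15 has an exact 95% upper limit of 1 − 0.025^(1/15) = 21.8%, so the pilot does not rule out any row of the table.

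**The case against.** The best defence is that the Missing Data section already settles the matter. It sits in the Analysis Plan, defines the set formally and ties imputation to it. It also says non-adherence is not a reason for discontinuation. Strictly read, the Randomization Procedures sentence gives only a sufficient condition: attenders are in, and nothing is said about non-attenders. Dropout is mentioned in the same paragraph as the full set, and the intervention groups are formed by randomisation. On this view only a wording mismatch remains, in a trial that describes its evidence as preliminary.

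Part of this stands. Missing Data is the likelier statement of intent, and it ties dropout loosely to the full set. But if everyone randomised is included anyway, the attendance clause has no function. The document does not say that the other section prevails.

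Two further objections also have weight:

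- **The figures are hypothetical.** The counts of never-starters are assumed, non-completion is not the same as leaving the study, and no between-arm effect is demonstrated. The table shows sensitivity and predicts nothing. The conflict does not depend on it.
- **Including never-starters raises practical questions.** Both later assessments are timed from a final session they do not have. They have no homework to complete, and the satisfaction scale rates a therapist they never met. These points need a line each, but they do not justify removing people from ITT.

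**Conclusion.** The concern holds and should be fixed. Two current sections define ITT differently, nothing reconciles them, and one, on its natural reading, conditions on an event after randomisation that is part of a primary-aim outcome. The Missing Data definition is the sound one.

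This rests on the text and on the order of randomisation and session 1, not on any assumed rate. The size is unknown and may be zero. Under the stated assumptions, reported dropout would fall from 25.0% to between 24.2% and 14.3% with 1 to 12 never-starters. The largest effect is on Aim 2. For Aim 1, bias is possible only if never starting differs between arms, and the documents do not address that.

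**What to change.** 1. **Randomization Procedures:** delete the five-word clause requiring attendance at session 1, so that ITT means all randomised participants analysed as assigned, in line with Missing Data.
2. **Feasibility and Acceptability Analyses:** add a sentence stating that dropout and attendance use all randomised participants as the denominator. Never-starters count as attending zero sessions and are included in dropout. Their number per arm may also be shown separately.
3. **For clarity:** say how homework completion and the STTS-R are handled for people who attended no sessions, and confirm that their missing efficacy outcomes fall under the multiple imputation already planned.
4. **Optional:** if a set limited to session 1 attenders is reported, call it modified ITT and use it only as a sensitivity analysis.

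The cost is one deletion and a few added sentences, with no new data. Dropout figures may look slightly less favourable, and a few more outcomes may need imputing.
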